## 16. EFFICACY OUTCOMES

All efficacy analyses will be performed based on the mITT, unless otherwise indicated. Observed and changes from Baseline will be summarized by treatment group. No summaries for all JZP-110 doses pooled into one group will be presented for any efficacy endpoints. Summaries for CGIc, PGIc, MDS-UPDRS, Apathy, FSS, and SCOPA-Cog will be broken down further by sequence for the placebo treatment group.

For subjects randomized into Sequence C, the average of the non-missing values collected at the end of each treatment period will be used in the computation of the descriptive statistics, but the individual period values will be used in the statistical inferences for all efficacy endpoints, exception of CGIc and PGIc. For CGIc and PGIc, the assessment collected at the end of treatment period 1 will be used for the summaries

and statistical inferences.

## **16.1. KEY EFFICACY ENDPOINT**

### **16.1.1. KEY EFFICACY ENDPOINT & DERIVATION**

The key efficacy endpoint is defined in terms of change from study Baseline to the end of treatment period.

The ESS is a self-administered questionnaire with 8 questions asking the subject how likely they would be to doze off or fall asleep in different situations. Responses range from “0 = would never doze” to “3 = high chance of dozing”. Subjects will be asked to complete the ESS with regard to the level of sleepiness they experienced over the past 7 days at Screening, Baseline, Visits 3, 4, 5, and 6, and at the Safety Follow-up visit. The ESS provides a measure of a person’s general level of sleepiness, or their average sleep propensity in daily life. It is a validated measure with high specificity and sensitivity for assessing subjective sleepiness.

The ESS total score is the sum of the 8 individual question scores. If three or more question scores are missing at a specific time point, the ESS total score will be set to missing. If one or two ESS question scores are missing at a specific time point, the mean of the remaining seven or six non-missing ESS question scores at that time point will be used to impute the missing ESS item scores. The ESS total score will be then calculated as the sum of the observed and imputed item scores.

### **16.1.2. HYPOTHESIS TESTING**

Given that the primary objective of the study is safety, no formal hypothesis will be tested for any safety endpoints.

[figure not shown]
To address the secondary objective of the efficacy of JZP-110 in the treatment of excessive sleepiness (i.e., the key secondary efficacy endpoint of change from Baseline in ESS total score to the end of treatment period), pairwise treatment difference against placebo will be tested as part of the mixed-effects model described in Section 16.1.4 using a 2-sided test at 0.05 level. No formal hypothesis will be tested for the key secondary efficacy endpoint since the sample size computations were performed for reference only (see Section 3.4) and nominal p-values will be provided.

[figure not shown]
### **16.1.3. MISSING DATA METHODS FOR KEY EFFICACY ENDPOINT 7**

Missing ESS total score will not be imputed.

#### 16.1.5. SENSITIVITY ANALYSIS OF KEY EFFICACY ENDPOINT

- **Sensitivity to carry-over effect from the end of period 3 to end of period 4 in Sequence B** (i.e., from JZP-110 300 mg to placebo): ESS total score observed values at end of treatment period for Period 3 and end of treatment for Period 4 for subjects randomized into Sequence B as well as the change from Baseline to each end of the treatment period will be summarized using descriptive statistics by treatment group based on the mITT.

The key efficacy analysis will be repeated adjusting the model for carry-over effect of Period 3 on Period 4, by adding an effect-type coding variable for the 4 treatment groups representing the residual treatment effect of the treatment taken during the previous period as fixed effects (Kuehl, 2000):

Treatment Group	Residual effect of JZP-110 300 mg, x
JZP-110 75 mg	0
JZP-110 150mg	0
JZP-110 300 mg	1
Placebo	-1

In other words, if a subject is randomized to Sequence A (i.e., placebo, JZP-110 75 mg, JZP-110 150 mg, and JZP-110 300 mg), the variable x will be set to the following on Period 4 subject record to represent the treatment group with which the subject was treated during the previous period (i.e., JZP-110 150 mg): x = 0. If a subject is randomized to Sequence B (i.e., JZP-110 75 mg, JZP-110 150 mg, JZP-110 300 mg, and placebo), the variable x will be set to the following on Period 4 subject record to represent the treatment group with which the subject was treated during the previous period (i.e., JZP-110 300 mg): x = 1. Finally, if a subject is randomized to Sequence C (i.e., placebo, placebo, placebo, and placebo), the variable x will be set to the following on Period 4 subject record to represent the treatment group with which the subject was treated during the previous period (i.e., placebo): x = -1.

Log Likelihood and degrees of freedom for each model (adjusted and not adjusted for carry-over effect) will be presented. To assess the significance of the carry-over effect, a likelihood ratio test will be performed as follows: the difference of the ‘-2 residual likelihood fit statistic’ (-2logL) between the 2 models (i.e., -2logL of model no adjusted - -2log L of adjusted model) will be tested using a Chi-square test at 0.05 alpha level with a degree of freedom defined as the difference between degrees of freedom of model adjusting for carryover effect minus degrees of freedom of model not adjusting for carryover effect.

Should the carryover effect be statistically significant, the key efficacy analysis will be repeated, but excluding period 4 data of subjects randomized to Sequence B.

- **Sensitivity to carry-over effect from the end of period 4 to safety follow-up period in Sequence A** (i.e., from JZP-110 300 mg to not treated with neither JZP-110 nor placebo): Observed values at end of treatment period for period 4 and end of safety follow-up period for subjects randomized into Sequence A as well as change from Baseline in ESS total score to the end of each period will be summarized using descriptive statistics by treatment group based on the mITT. No statistical inferences will be performed.
- **Sensitivity to treatment-by-sequence interaction:** Given the study design, the treatment-by-sequence interaction is aliased with the period effect included in the main model. Hence, p-value for the period effect obtained from the primary analysis of the key efficacy endpoint will be provided.

- **Sensitivity to analysis population:**
  - The key efficacy analysis will be repeated based on the EFF.
  - The key efficacy analysis will be repeated based on the PP.

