### **3.4. SAMPLE SIZE JUSTIFICATION**

[figure not shown]
Approximately 49 subjects will be randomized to the 3 sequence groups (A, B, and C) with the goal of 40 subjects completing the study: 34 subjects in Sequences A and B, and up to 6 subjects in sequence C. The randomization ratio implemented will be 3:3:1 with expected randomization of subjects to sequences being approximately 21:21:7.

Although the primary objective of this study is to assess safety, efficacy endpoint-based power calculations were performed for reference. A sample size of 34 subjects (assuming 17 completing in each of the Sequences A and B) will provide 80% power to detect a difference of 3 points in the change from Baseline in ESS score between 1 of the JZP-110 and placebo groups not adjusting for multiple comparisons. This calculation assumes a common standard deviation (SD) of 6 points for the change from Baseline in ESS score and a 2-sided significance level of 0.05 using an analysis of variance (ANOVA)-based t-test for difference of means in a crossover design. The primary purpose of placebo Sequence C is to preserve study blinding.

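### SAP 16.1.5 tests carry-over by comparing REML likelihoods of models with different fixed effects; at the planning values it would flag carry-over in about 26% of trials that have none

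*SAP*

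**What the plan says.** The key ESS model in SAP 16.1.4 has baseline ESS, treatment, sequence and period as fixed effects and a random subject effect, fitted with PROC MIXED on the mITT (Sequences A, B and C).

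SAP 16.1.5 repeats that model with one extra fixed effect, x, for the treatment of the preceding period: 1 after 300 mg, −1 after placebo, and 0 after 75 or 150 mg. The text gives its value only for the last period ("the variable x will be set to the following on Period 4 subject record"): A = 0, B = 1, C = −1.

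The test is then described: "To assess the significance of the carry-over effect, a likelihood ratio test will be performed as follows: the difference of the" minus-two residual log likelihoods ("2 residual likelihood fit statistic") of the two models "will be tested using a Chi-square test at 0.05 alpha level with a degree of freedom defined as the difference between degrees of freedom" of the two models. No ML refit is specified.

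The consequence is also fixed in advance: "Should the carryover effect be statistically significant, the key efficacy analysis will be repeated, but excluding period 4 data of subjects randomized to Sequence B".

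**The concern.** The two models differ only in a fixed effect. The residual likelihood contains log|X′V⁻¹X| and a constant based on N − p, and both change when a column is added to X. The difference between the two fits is therefore not a likelihood-ratio statistic for x and does not follow chi-square.

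The result matters because Protocol 3.2 leaves out a washout, so Sequence B goes straight from 300 mg to placebo, and Protocol 9.12 leaves the carry-over methods to the SAP. This is the SAP's only inferential check on carry-over; the comparison of Sequence A's Period 4 with follow-up is descriptive. A flag removes Sequence B Period 4, which is all of Sequence B's placebo data. The dose–placebo contrasts are then separable from period only through the six or so Sequence C subjects.

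**Working it through.** **Inputs.** From SAP 3.4: 17 + 17 completers in A and B, up to 6 in C; 21:21:7 randomised; a 3-point difference; SD 6; two-sided 0.05; 80% power. The models and coding come from SAP 16.1.4 and 16.1.5. Two assumptions fill gaps in the SAP: x = 0 in Periods 1–3, and df = 1.

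**Residual SD.** The SAP says "This calculation assumes a common standard deviation (SD) of 6 points for the change from Baseline in ESS score" but gives no within-subject correlation. A paired t-test with n = 34 and difference 3 gives:
- SD of the within-subject difference 6 (equivalently SD 6 per measurement with correlation 0.5): power 80.8%, which reproduces the stated 80%.
- SD 6 per measurement with correlation 0 (SD of the difference 8.49): power 51.7%.

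The planning values therefore imply a residual SD of 6/√2 = 4.24. This is inferred, so a range is given below.

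**Form of the statistic.** The REML difference is approximately W + log(2π·SEₓ²), where W is the Wald chi-square for x. The false-positive rate is P(χ²₁ > 3.84 − log(2π·SEₓ²)).

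**Planning case, 17/17/6.** Generalised least squares with treatment, sequence, period and random subject gives SEₓ = 1.463. Then log(2π × 1.463²) = 2.60 and 3.84 − 2.60 = 1.24, so P(χ²₁ > 1.24) = 26.5%. Simulations of the full REML fit with the baseline covariate and no carry-over gave 25.6% to 28.4%.

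**As randomised, 21/21/7.** SEₓ = 1.346, the offset is 2.43 and the threshold 1.41, giving 23.5% (simulated 23.2–24.8%).

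**Range at 17/17/6, closed form.**

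| Residual SD | SEₓ | False-positive rate |
|---|---|---|
| 2 | 0.69 | 9.7% |
| 3 | 1.03 | 16.4% |
| 4.24 | 1.46 | 26.5% |
| 5 | 1.72 | 33.9% |
| 6 | 2.07 | 45.8% |

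If x were coded in every period, the simulated rate would be about 34–36% (17/17/6) or 31–32% (21/21/7).

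**Dependence on units.** Dividing ESS by 10 changes nothing of substance, yet rejections fall to 1.9% and the statistic is negative in 84% of simulated trials. A chi-square variable cannot behave this way.

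**Valid tests.** At 17/17/6 the ML likelihood ratio test rejected in 5.3–7.3% of null simulations, and the t/F test of x in the REML fit in 4.6–5.7%.

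**Cost of a false alarm (17/17/6).** Standard errors of the 75/150/300 mg contrasts go from 1.20/1.36/1.20 in the primary model to 1.64/2.23/2.71 without Sequence B Period 4.

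**Power.** Suppose a carry-over c occurs only in Sequence B Period 4. Then x recovers 0.377c. For c = 3 the expected Wald z is 0.377 × 3 / 1.463 = 0.77, which gives about 12% power for a valid test; the REML rule flags about 40%.

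**Coding (secondary).** In that same scenario the 300 mg contrast carries a bias of 0.68c in magnitude unadjusted and 0.43c after adjustment for x. For c = 3, about 1.3 points remain. The 1/0/−1 coding does not isolate carry-over from 300 mg to placebo, because it also loads on Sequence C with the opposite sign.

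**The case against.** Four points deserve an answer.

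- **The 26% rests on an inferred correlation.** SAP 3.4 does not state one. That stands, and the rate should be quoted with its range. It is above 5% at every value tried, so the conclusion does not depend on the inference.
- **The consequence is limited.** The primary objective is safety, and for ESS "nominal p-values will be provided" without a formal hypothesis. The primary model is reported whatever the test shows, the model adjusted for x is fitted in every trial, and Sequence B's Period 3 and 4 values are summarised. All of this stands and limits the severity. A false alarm is still not harmless. With known variances and no drug effect or carry-over, the 300 mg contrast in the triggered refit is nominally significant in about 16–17% of flagged trials, against 5% for the primary analysis.
- **A valid test detects little.** With about 12% power for 3 points, it misses about 88% of such carry-overs. That is true. It does not rescue the REML rule, whose 40% detection comes with about 26% false alarms, but it is a good reason to report an estimate and interval.
- **The coding is a matter of choice.** The SAP takes it from a cited textbook, and under the scenario above it does reduce the bias from 0.68c to 0.43c. An alternative coding is a trade-off, so this is only a secondary point. Zero in Periods 1–3 is also the natural reading, although the SAP should say so.

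**Conclusion.** The concern holds. The test in SAP 16.1.5 is invalid as written, and no other section corrects it. Its false-positive rate is about 26% with 17/17/6 completers and about 23.5% with 21/21/7, against a nominal 5%. These figures assume a residual SD of 4.24 (inferred from the stated power), complete data, x = 0 in Periods 1–3 and df = 1. The rate is about 10–46% for residual SDs of 2 to 6. The effect is confined to a sensitivity analysis: about one trial in four without carry-over would report significant carry-over and print a supplementary table with much wider intervals. The primary ESS analysis does not change. It should be fixed before unblinding.

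**What to change.** In SAP 16.1.5:

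1. Report the estimate of the carry-over coefficient with its 95% CI. State that a non-significant result does not show absence of carry-over, since power is about 12% for 3 points.
2. Test x with the t or F test of its coefficient in the REML fit, or refit both models with METHOD=ML and use that likelihood ratio.
3. State df = 1 and the value of x in Periods 1–3.
4. Note that the 1/0/−1 coding does not isolate carry-over from 300 mg to placebo.

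This takes a few sentences and at most one SAS option, needs no new data and leaves the primary analysis as it is.

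Optionally, an indicator for Sequence B Period 4 could replace x in this sensitivity model. It is unbiased if carry-over occurs only there, but its cost should be disclosed. The standard error of the carry-over term is 3.55, power for 3 points reaches only about 13.5%, and the standard error of the 300 mg contrast rises from 1.57 (SAP coding) to 2.71, the same as excluding that cell.

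### SAP 16.1.5 repeats the ESS analysis without Sequence B's final placebo week only if a carry-over test is significant, and a valid test would have only about 10–22% power against even a worst-case carry-over

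*SAP*

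**What the plan says.** Protocol 3.2 explains that no placebo washout separates the periods. In Sequence B the only placebo observation therefore follows directly on a week of 300 mg. SAP 16.1.5 addresses this in three steps.

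- **Always done:** ESS in Sequence B at the ends of Periods 3 and 4 is summarised descriptively.
- **Always done:** the key model of SAP 16.1.4 (baseline, treatment, sequence, period, random subject within sequence) is refitted with a carry-over variable x. On Period 4 records x is 1 for Sequence B, 0 for Sequence A and -1 for Sequence C. Then "To assess the significance of the carry-over effect, a likelihood ratio test will be performed", by comparing the -2 residual likelihoods of the two models with a chi-square distribution at the 0.05 level.
- **Conditional:** "Should the carryover effect be statistically significant, the key efficacy analysis will be repeated, but excluding period 4 data" of Sequence B.

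Neither document gives the power of the carry-over test. The power statement in SAP 3.4 ("will provide 80% power to detect a difference of 3 points in the change from Baseline in ESS score") concerns a treatment comparison only.

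**The concern.** The exclusion analysis is the only planned inferential estimate that carry-over into Sequence B's placebo week cannot bias, and it is produced only if a significance test says so. If that test has little power, the analysis will usually be absent when it would be informative. If the test also fires often by chance, the analysis will appear for reasons unrelated to carry-over. Persistence of the 300 mg effect would make Sequence B's placebo week look better than placebo. All three dose effects would shrink, by different amounts, which also distorts the dose-response that Protocol 3.2 wants for later dose selection.

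**Working it through.** **Inputs (SAP 3.4).** "A sample size of 34 subjects (assuming 17 completing in each of the Sequences A and B"), "up to 6 subjects in sequence C", randomisation "3:3:1 with expected randomization of subjects to sequences being approximately 21:21:7", SD 6, difference 3 points, 2-sided 0.05. The within-subject correlation is not stated.

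**The plan's own figure.** Take 6 as the SD of the within-subject difference. The SE is 6/√34 = 1.029 and the noncentrality is 3/1.029 = 2.92, so power on 32 df is 80.7%, matching the stated 80%. Taking 6 as the within-subject SD gives 51.6%, which does not match. The matching reading equals a common SD of 6 with correlation 0.5, that is residual variance 36 × 0.5 = 18 and between-subject variance 18. I use this and vary the correlation.

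**Why Sequence C carries the information.** Let s be the Sequence B minus A effect, τ the effect of each dose against placebo, and λ the carry-over in Sequence B Period 4. The B minus A differences by period are:

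- P1: s + τ75
- P2: s + τ150 − τ75
- P3: s + τ300 − τ150
- P4: s − τ300 + λ

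They sum to 4s + λ, so A and B alone cannot separate λ from s (8 cell means, 8 parameters already in use). If λ is ignored, s is off by λ/4, and the dose effects are off by −λ/4, −λ/2 and −3λ/4. Adding Sequence C makes λ estimable, but only through 6 or 7 subjects.

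**Bias in the key model with Sequence C.** Generalised least squares on the 17/17/6 layout, without the baseline covariate: bias = (X′V⁻¹X)⁻¹X′V⁻¹c, where c marks Sequence B Period 4. Per point of λ this gives −0.315, −0.500 and −0.685 for 75, 150 and 300 mg. At λ = 3 the 300 mg bias is 0.685 × 3 = 2.05 points.

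**Power of a valid Wald test, correlation 0.5, 17/17/6.**

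- SAP coding: the coefficient has expectation 0.377 per point and SE 1.463. Noncentrality at 3 points is 3 × 0.377/1.463 = 0.77, so power is 12.0%.
- Plain indicator for Sequence B Period 4: SE 3.551, noncentrality 3/3.551 = 0.84, power 13.3%.
- At 1.5 points, power is 7% with either. For 80% power λ would have to be about 10–11 points.

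Power at 3 points (SAP coding / indicator):

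| Correlation | 17/17/6 | 21/21/7 |
|---|---|---|
| 0.3 | 10% / 11% | 11% / 12% |
| 0.5 | 12% / 13% | 13% / 15% |
| 0.7 | 17% / 19% | 19% / 22% |

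**The test as written.** Residual likelihoods of models with different fixed effects are not comparable. With variances taken as known, the difference equals Wald² + log(2π·Var). Here log(2π × 1.463²) = 2.60, so the test fires when Wald² > 3.84 − 2.60 = 1.24. That happens in about 26% of trials with no carry-over, 30% at 1.5 points and 40% at 3 points. A simulation with estimated variances (3,000 runs) gave 28% with none and 40% at 3 points.

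**What the always-fitted adjusted model achieves.** With x = −1 for Sequence C, the 300 mg bias falls from 0.685 to 0.426 per point. With a plain indicator it is 0, and the estimates and SEs equal those from deleting Sequence B Period 4. I set x to 0 in Periods 1–3, since the SAP's worked examples define it only for Period 4. Applying the SAP's coding table in every period leaves 0.50 per point.

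**Price of the exclusion analysis (17/17/6).** The 300 mg SE rises from 1.20 to 2.71 (CI about ±5.4), and power for a 3-point 300 mg effect falls from about 70% to 20%. In Sequences A and B alone it cannot be estimated (rank 7 for 8 parameters).

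**The case against.** Several stronger readings are tempting, and the documents do not support them.

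- **That the placebo week is contaminated.** This is a hypothesis. Protocol 1.3.1 gives a half-life of 5–7.6 hours with at least 90% excreted within 48 hours, and Protocol 3.2 reports no carry-over in the Phase 2a narcolepsy crossover. If, for illustration, the effect lasted five half-lives (25–38 hours), it would touch 15–23% of the 7-day (168-hour) ESS recall. On a 3-point effect that is about 0.45–0.7 points of carry-over, and a 300 mg bias of 0.3–0.5. Three points is an upper bound.
- **That nothing addresses carry-over unless the test is significant.** The adjusted model and the Sequence B summaries are unconditional. So are the ESS summaries by sequence and period and the descriptive look at Sequence A after 300 mg.
- **That the test selects the primary data.** It only adds a sensitivity run; the analysis of SAP 16.1.4 stands either way. Nor does the SAP say that a non-significant result will be read as no carry-over, although a reader may take it so.

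Two further points stand. At correlation 0.5 the exclusion estimate is so imprecise that, even with 3 points of carry-over, its root mean squared error for 300 mg (2.71) exceeds that of the key model (√(2.05² + 1.20²) = 2.38). And ESS is a secondary, exploratory endpoint with nominal p-values, with a bias toward zero. These points limit the size of the concern. They do not justify the condition: the adjusted model as coded keeps about 62% of the 300 mg bias (0.426/0.685), and the test barely separates carry-over from none.

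**Conclusion.** The condition should go. A valid test has roughly 10–22% power against the upper-bound 3-point carry-over, and the test as written fires in about 40% of cases at 3 points against 26–28% with none. Neither result is a sound basis for deciding whether to show the exclusion analysis. At stake is a pull toward zero of about 0.32, 0.50 and 0.69 points per point of carry-over for 75, 150 and 300 mg, probably small in practice given the half-life and the Phase 2a finding. The figures assume complete data at the stated completer numbers, SD 6, correlations of 0.3–0.7 (my assumption) and no baseline covariate. This is a modest, inexpensive correction to a sensitivity analysis; it does not invalidate the primary ESS estimate.

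**What to change.** In SAP 16.1.5, delete the condition. State that the key analysis will always be reported, as a sensitivity analysis, with and without Sequence B Period 4, side by side with 95% CIs. Refitting with a plain Sequence B Period 4 indicator is equivalent. Add three statements:

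1. A non-significant carry-over test is not evidence of no carry-over.
2. The exclusion analysis relies on Sequence C and cannot be estimated in the EFF (Sequences A and B only, SAP 5.3).
3. It is a check for bias, to be read from its estimate and interval, and does not replace the primary estimate.

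If the indicator is used and a test is kept, take it from the Wald or F statistic. The residual-likelihood difference would then always exceed the cut-off, because log(2π × 3.551²) = 4.37 is already above 3.84.

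The cost is a change of wording, one more model run and a wide interval (300 mg SE about 2.7 against 1.2). Design and conduct are unaffected.
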